3.3 Definition of dose limiting toxicity

Some of the dose limiting toxicity (DLT) and maximum tolerated dose (MTD) definitions are derived from the National Cancer Institute (NCI) Common Terminology Criteria for Adverse Events (CTCAE) Version 4.02. Please note that not all of the events described as DLTs are fully supported by NCI CTCAE but are formed by amalgams of different events in order to assist with assessments of adverse events.

The definition of DLT applies to both the single agent and combination dose escalation arms (Part A of the study [boxes outlined in red in Figure 2]).

A DLT is defined as a highly probably or probably **BI-1206 or rituximab-related AE occurring during** the four weeks of induction treatment and up to one week post the fourth infusion of BI-1206 (i.e. by Day 28/Week 5) which fulfils one or more of the following criteria:

- Neutropenia or neutrophil count decrease Grade 4 ($ANC < 0.5 \times 10^9/L$) for >10 days duration
*see note despite growth factor support
- Febrile neutropenia (fever of unknown origin without clinically or microbiologically documented infection) with Grade 3 or 4 neutropenia (absolute neutrophil count [ANC] $<1.0 \times 10^9/L$) and fever $\geq 38.5^\circ C$).
- Infection (documented clinically or microbiologically) with Grade 3 or 4 neutropenia ($ANC < 1.0 \times 10^9/L$)
- Thrombocytopenia or platelet count decrease Grade 4: a) for ≥ 5 days*see note, or b) associated with active bleeding, or c) requiring platelet infusion
- Grade 3 or 4 non-haematological toxicity. This includes Grade 3 and 4 biochemical AEs as DLTs.

EXCLUDING:

- Grade 3 or 4 nausea or vomiting in patients who have not received optimal treatment with anti-emetics
- Grade 3 or 4 diarrhoea in patients who have not received optimal treatment with anti-diarrhoeals
- Alopecia
- Grade 3 infusion related reactions
- Transient, asymptomatic Grade 3 biochemical abnormalities if agreed by the Sponsor and the study team, including the Chief Investigator
- Event with a fatal outcome.

***Note: In the event of a Grade 4 neutropenia or Grade 4 thrombocytopenia, a full blood count must be performed at least on Day 10 (Day 5 for thrombocytopenia) after the onset of the event to determine if a DLT has occurred. The investigator must continue to monitor the patient closely until resolution to Grade 3 or less. Please See [Section 5.9.4](#) 'Management of thrombocytopenia (Grade 4)' for further details.**

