5.9.4 Management of thrombocytopenia (Grade 4)

If Grade 4 thrombocytopenia is noted post infusion:

- Perform daily (or as frequent as possible) full blood count (FBC) monitoring until resolution to Grade 3 or less.

- If this is not possible, then the patient should be monitored closely until resolution to Grade 3 or less AND as a minimum a FBC must be performed on the 5th day from when Grade 4 thrombocytopenia was first noted (unless there is documented resolution to Grade 3 before that point).
- Toxicity must be resolved to at least Grade 2 or lower before the next dose can commence; therefore a delay in treatment may be required.

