Premedication (h)			X		X		X		X		X			X (i)		
BI-1206/ rituximab administration (h)			X		X		X		X		X			X (i)		
PK sampling (see Section 8)			X	X	X	X	X	X	X	X	X			X		
PD sampling (see Section 8)		X	X	X (o)	X	X (o)	X	X (o)	X	X (o)	X		X	X	X	
Follow-up contact for survival/progression (n)																X

(a) In patients that are refractory to rituximab, i.e either progressing whilst on rituximab based therapy (induction or maintenance) or progressing within 6 months of their last dose of rituximab, a biopsy should be performed prior to study entry to ensure that there is continued expression of CD20.

(b) Pregnancy test: For female patients of child bearing potential within 2 weeks before receiving BI-1206.

(c) Weight measured during screening should be used for BSA calculation for induction therapy. For maintenance treatment, weight should be measured prior to each dose and BSA recalculated if the patient's weight has changed by more than 10% from the weight used for the current BSA (i.e. weight at 1st maintenance will be compared to weight measured at screening), there is no need to re-measure height.

(d) Complete physical examination to be performed pre-study then all subsequent examinations can be symptom-directed or as clinically indicated.

CONFIDENTIAL

(e) Clinical laboratory assessments should be performed prior to each BI-1206 infusion (and before each rituximab administration if given on a different day to BI-1206). Laboratory tests can be performed up to 24 h prior to each infusion but results must be available and reviewed by the investigator before BI-1206/rituximab is given. In the event of a Grade 4 neutropenia or Grade 4 thrombocytopenia a full blood count must be performed at least on Day 5 (Day 10 for neutropenia) after the onset of the event to determine if a dose limiting toxicity has occurred. Monitoring must continue until resolution to Grade 3 or less. At screening, GFR measurement may be required if there is a concern regarding the calculated creatinine clearance measurement).

If split dosing is implemented, laboratory tests will be relative to the first infusion administered each week then as clinically indicated on the second day.

(f) Eye exam, performed by ophthalmologist to be performed at screening, week 8 and off-study and otherwise as clinically indicated.

(g) ECG to be performed pre-study and otherwise as clinically indicated.

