(h) For patients recruited to Part A & B, Arm 2, rituximab to be given on Day 2 post BI-1206 at Week 1. If infusion time permits, then subsequent doses of rituximab will be given on the same day as BI-1206. Maintenance treatment (from Week 8) will only be given if a patient is deemed eligible to continue on to maintenance treatment following Week 8 assessments.

If split dosing is implemented, laboratory tests will be relative to the first infusion administered each week then as clinically indicated on the second day.

(i) Maintenance therapy will only be given to those patients who demonstrate stable or responding disease and will start after the Week 8 scan results following induction therapy confirming patient is eligible for maintenance treatment. Patients will receive the same dose of BI-1206 (and rituximab if received) as in their induction therapy from week 8 onwards (i.e. Week 9 or 10) and every 8 weeks (\pm 2 weeks) from the first maintenance dose, for up to one year from first induction dose.

(j) A CT scan to assess the patient's tumour burden to be performed at Week 8 (prior to commencing maintenance therapy) and then every 16 weeks (\pm 2 weeks) during maintenance therapy and at off-study. Patients with Waldenstrom's macroglobulinaemia will also have serum paraprotein samples taken at these time points. If a complete response is noted, a bone marrow biopsy may be performed and in a lymphoma patient with PET-avid disease a FDG-PET scan will also be performed. A scan is only required at Off-study if no appropriate disease assessment has been performed recently (at week 8 or as required on maintenance).

(k) Monthly follow-up required ONLY for those AEs and SAEs considered drug-related (highly probable, probable or possible) and present at off-study. Monthly follow-up for AEs to continue until resolution, return to baseline, stabilisation or patient starts another anti-cancer treatment.

(l) Day 11, 18, 25 assessments performed for patients in Cohort 1, Arm 1 only.

(m) Bone marrow aspirate samples are used for pharmacodynamic analysis, trephine samples are to be taken where required for disease assessment, if a sample is taken as part of routine care within 8 weeks prior to starting on the study a repeat baseline sample is not required. After baseline, a bone marrow sample is only required for disease assessment to confirm at complete response.

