8.3.1.1 Pharmacokinetic sampling, Part A, Arm 1 single agent BI-1206

During intra-patient dose escalation (one patient): a 6 mL blood sample will be taken pre-infusion, at end of infusion (EOI) (+5 mins) and at 4 hours (± 15 mins), 24 hours (± 1 hour), 48 hours (± 1 hour) and 72 hours (± 5 hours) post the end of infusion for every BI-1206 administration during induction therapy.

CONFIDENTIAL

From Cohort 2 onwards (Part A, Arm 1): a 6 mL blood sample will be taken pre- infusion, at end of infusion (+5 mins) and at 4 hours (± 15 mins), 24 hours (± 1 hour), 48 hours (± 1 hour) and 72 hours (± 5 hours) post end of infusion following dose 1 (Week 1) and then again at the same time points prior to and following the patient's fourth dose (Week 4). A 6 mL blood sample will also be taken prior to the BI-1206 infusions at Weeks 2 and 3 (Table 3).

The approximate volume of blood withdrawn from each patient receiving BI-1206 alone for pharmacokinetic analysis will be 84-144 mL during the induction period (8 weeks) with an additional 36 mL withdrawn over the subsequent maintenance treatment period.

All patients who receive maintenance therapy will have 6 mL blood samples taken prior to each infusion (every 8 weeks).

Table 3: Part A, Arm 1 PK sampling schedule

Time	Part A: Cohort 1 (Intra-patient dose escalation)					Part A : From Cohort 2 onwards				
	Induction				Maintenance	Induction				Maintenance
	Week 1	Week 2	Week 3	Week 4	Every 8 weeks	Week 1	Week 2	Week 3	Week 4	Every 8 weeks
Pre	X	X	X	X	X	X	X	X	X	X
EOI	X	X	X	X		X			X	
+4hrs	X	X	X	X		X			X	
+ 24hrs	X	X	X	X		X			X	
+48hrs	X	X	X	X		X			X	
+ 72hrs	X	X	X	X		X			X	
Total per patient (mL)	144				(up to 36)	84				(up to 36)

For **split dosing administration** of single agent BI-1206:

- **Part A: Cohort 2 onwards:** up to 18 PK time points may be taken during the induction period (8 weeks) with an additional 6 PK timepoints thereafter (to include pre-infusion sampling during the maintenance phase). This will be approximately 108 mLs taken over the first eight weeks with approximately 36mLs taken post the induction phase, throughout the maintenance phase.
- If split dosing is implemented, the blood volume requested will not exceed the maximum volume noted above i.e. 144 mL.
- Please refer to the study laboratory manual for handling, adjusted sample times, sample volume per time point, storage and shipment of samples.

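### From Cohort 2, blood counts after Day 8 are 7 days apart, so a silent Grade 4 platelet fall of 5 or 6 days that would be a DLT can go unseen; day-counting for both duration-based DLTs is also undefined

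*Combined protocol and SAP*

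**What the plan says.** Two DLT criteria in Section 3.3 depend on duration. One is "Thrombocytopenia or platelet count decrease Grade 4: a) for ≥ 5 days" (bleeding or platelet infusion makes Grade 4 a DLT at any duration). The other is Grade 4 neutropenia "for >10 days duration" despite growth factor support. The note to Section 3.3 fixes the deciding count: "a full blood count must be performed at least on Day 10 (Day 5 for thrombocytopenia) after the onset of the event". It then adds: "The investigator must continue to monitor the patient closely until resolution to Grade 3 or less". Section 7.6 note (e) repeats the rule: "a full blood count must be performed at least on Day 5 (Day 10 for neutropenia) after the onset of the event".

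For thrombocytopenia, Section 5.9.4 first asks for daily counts, or as near to daily as can be managed. Where that is not possible, "as a minimum a FBC must be performed on the 5th day from when Grade 4 thrombocytopenia was first noted". Neutropenia has no corresponding section.

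Section 7.2 schedules induction haematology before each BI-1206 dose, before rituximab when it falls on another day, on Day 4 of Week 1, and at Weeks 5 and 8. Mid-week counts in Weeks 2 to 4 are restricted by Section 7.6 note (l): "Day 11, 18, 25 assessments performed for patients in Cohort 1, Arm 1 only".

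Pharmacokinetic sampling is wider. From Cohort 2 in Arm 1 the full series, including 72 hours after infusion, is taken after dose 1 "and then again at the same time points prior to and following the patient's fourth dose (Week 4"; see Table 3. Table 5 also has a Week 4 72-hour sample for Arm 2.

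**The concern.** A criterion met in 5 days is being watched, in most of Part A, by counts 7 days apart. The close follow-up in Sections 3.3 and 5.9.4 begins only after a Grade 4 count has been seen, so it cannot help with a fall that starts and recovers between two scheduled counts.

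The DLT count is the Part A primary endpoint, and two DLTs at a dose level define the MAD (Section 3.4.1). Section 2.2.8 lists thrombocytopenia as a risk because of data from this trial. Cohorts 2 to 4 may hold a single patient while the dose doubles at each step from 100 mg to 800 mg (Table 1). One unseen event could therefore leave both the DLT rule and the Grade 2 expansion trigger of Section 5.4.2 inactive. The error runs one way, towards fewer DLTs and a higher recommended dose.

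There is a smaller problem after detection. The protocol does not say how days are numbered, and its sections start the thrombocytopenia clock at different points.

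**Working it through.** The plan states no detection probability, so there is no figure to reproduce.

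**1. Unseen platelet falls.** Let a fall start on day s and last L calendar days (s to s+L−1). Between consecutive counts on days a and b it is unseen if a+1 ≤ s ≤ b−L, so the number of unseen onset days is b−a−L, or zero if that is negative.

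- Gap 7: 7−5 = 2 for a 5-day fall; 7−6 = 1 for a 6-day fall; 7−7 = 0 for a 7-day fall.
- Gap 6: 1, 0, 0. Gaps of 3 or 4: none.
- Gap 10: 5, 4, 3.

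| Count days | 5-day fall: unseen onset days | 6-day fall: unseen onset days |
|---|---|---|
| Cohort 1, Arm 1: 1, 4, 8, 11, 15, 18, 22, 25, 29 | none | none |
| Cohort 2 on, or Arm 2 same-day: 1, 4, 8, 15, 22, 29 | 9, 10, 16, 17, 23, 24 (6 of 28) | 9, 16, 23 (3 of 28) |
| Arm 2, next-day rituximab: 1, 2, 4, 8, 9, 15, 16, 22, 23, 29 | 10, 17, 24 (3 of 28) | none |
| Cohort 2 on, Week 5 visit at Day 32 | 9, 10, 16, 17, 23–27 (9 of 28) | 9, 16, 23–26 (6 of 28) |
| Cohort 2 on, with a Day 25 count | 9, 10, 16, 17 (4 of 28) | 9, 16 (2 of 28) |

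With uniform onset within a 7-day interval, the shares are 2/7 = 28.6% and 1/7 = 14.3%. Day 32 is allowed because Section 7.6 gives Week 5 as Day 29 with up to 3 days' grace. Of the onsets unseen in that case, Days 25 to 27 reach a fifth calendar day only on Days 29 to 31. Section 3.3 ends the window at Day 28/Week 5 and does not say whether onset or completion must fall inside it.

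**2. Neutropenia.** An 11-day episode is longer than any gap above (7−11 and 10−11 are negative), so it is never wholly missed. The question is what a Grade 4 result on Day 10 proves:

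- Day 10 is onset+10, calendar days inclusive: 11th day, so more than 10 is shown.
- Onset is Day 1: 10th day, so it is not shown.
- Elapsed days: exactly 10, so it is not shown.

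A result of Grade 3 or less on Day 10 excludes the DLT for a continuous episode.

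**3. Thrombocytopenia anchor.** Section 3.3 and note (e) count from onset; the fallback in Section 5.9.4 counts from first detection. At weekly counts detection can lag onset by up to 6 days (onset Day 9, noted Day 15). Reading the fifth day as onset+4 or onset+5 changes the answer only for an episode of exactly 5 calendar days.

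**4. Possible effect on escalation (assumed inputs).** The probability that a 3+3 cohort escalates is (1−p)³ + 3p(1−p)⁵. The documents give no DLT rate. Assume p = 0.33, with 25% to 100% of DLTs being 5-day platelet falls and 2/7 of those missed. The observed rate is then 0.33 × (1 − 0.25 × 2/7) = 0.306 down to 0.33 × (1 − 2/7) = 0.236. Escalation probability rises from 0.43 to between 0.48 and 0.63. With p = 0.20 it rises from 0.71 to between 0.74 and 0.83. The upper ends are extreme, since they make every DLT a silent 5-day fall.

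**The case against.** A reader might infer that the mandated counts cannot decide the duration-based DLTs at all. The documents do not support that. Day 10 is a minimum, monitoring must continue until Grade 3 or less, a recovered Day 10 count does decide, and one reading of Day 10 is sufficient. What remains is that neither a day-numbering convention nor a count interval after Day 10 is given for neutropenia.

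A reader might also infer that the sections set different count days for thrombocytopenia. All three say day 5; only the starting point differs. Section 5.9.4 puts daily counts first, so a detected fall can normally be timed.

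On the 7-day gap, the fair objections concern scope. It does not touch Cohort 1 of Arm 1, it shrinks with next-day rituximab, and bleeding, platelet infusion or an unscheduled count would reveal the fall. Uniform onset is an assumption. The Day 4 count in Week 1 may reflect where falls are expected, but the documents give no timing. Against that, the unseen onset days fall one or two days after a weekly dose. Finally, the recommended dose also rests on cumulative toxicity and PK/PD data (Sections 3.3 and 3.4), which dilutes the effect of one missed DLT. These points limit the size of the problem; they do not close the gap.

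**Conclusion.** The point holds in a limited form. Outside Cohort 1 of Arm 1, the scheduled counts after Day 8 can miss a silent, untransfused Grade 4 platelet fall that meets the DLT definition: 2 of 7 onset days for a 5-day fall and 1 of 7 for a 6-day fall, or 1 of 7 and none with next-day rituximab. Falls of 7 days are always seen if visits are on time; a Week 5 visit at Day 32 opens a 10-day gap in which even some of these are missed. The shares assume uniform onset, on-time visits and no unscheduled count.

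The neutropenia timing and the thrombocytopenia anchor are ambiguities to be settled, not proof that DLTs cannot be determined. The effect on the MTD or recommended dose is upward in direction, but its size cannot be derived from the documents; the escalation figures are illustrative only.

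**What to change.** Leave the DLT thresholds as they are and change how they are ascertained.

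1. Amend Section 7.2 and Section 7.6 note (l) to add a full blood count on Day 25 for all Part A patients, at the existing 72-hour pharmacokinetic attendance (Day 22 + 72 hours). The cost is one tube. This closes the Week 4 gap only: unseen onset days for a 5-day fall go from 6 to 4 of 28. If Week 5 slips to Day 32, the interval from Day 25 is again 7 days and onsets on Days 26 and 27 stay unseen.
2. Decide openly whether to close Weeks 2 and 3 as well. Counts on Days 11, 18 and 25 bring unseen onset days to 0 of 28 with on-time visits, but no pharmacokinetic visit exists on Days 11 and 18 from Cohort 2. The added visit burden must be acknowledged, except where the optional samples in Section 7.6 note (o) already bring the patient in.
3. In Section 3.3 and note (e), require that neutropenia still at Grade 4 on Day 10 has a further count on Day 11 after the first Grade 4 count. With item 4, this lets the rule of more than 10 days be decided.
4. Reconcile Sections 3.3, 5.9.4 and 7.6 note (e) to one anchor and one day-counting convention (elapsed or inclusive).

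The counts need a protocol amendment: Sections 5.3.2 and 8 let dose meetings alter PK/PD sampling only without adding blood volume or burden. The other downside is that slightly more DLTs may be counted.

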3.4 Definition of maximum tolerated dose

3.4.1 Part A, Arm 1:Single-agent dose escalation

If two out of up to six patients at the same dose level experience a DLT as defined in Section 3.3, this dose level of BI-1206 will be considered the maximum administered dose level (MAD) and no further patients will be treated at this dose level. In this case, the maximum tolerated dose (MTD) will be determined as a dose level below the MAD, which could be a dose previously administered or an intermediate dose between a dose already administered and the MAD. This MTD will be agreed following the review of all the relevant toxicity data between the Sponsor and the study team, including the Chief Investigator.

The MAD could also equal the MTD in the event that dose escalation is stopped before two DLTs are observed at a given dose level due to the expectation that higher dose levels would be too toxic to administer to patients, or if the 800 mg dose level is reached.

The RP2D in Part A, Arm 1 which will be used in Part B, Arm 1 of the clinical trial, will be determined by the Sponsor, Chief Investigator and Principal Investigators, following review of all relevant pharmacokinetic/pharmacodynamic (PK/PD) and clinically relevant toxicity data for all patients entered onto the trial in Part A Arm 1, and the identified MTD or MAD. All significant toxicities and available data from Part A, Arm 2 and data from any other trials investigating BI-1206 will also be considered in the determination of the RP2D.

3.4.2 Part A, Arm 2: Combination dose escalation

The MTD and MAD of BI-1206, when given in combination with rituximab and will be defined as above (Section 3.4.1).

The MAD could also equal the MTD in the event that dose escalation is stopped before two DLTs are observed at a given dose level due to the expectation that higher dose levels would be too toxic to administer to patients, or if the 800 mg BI-1206 dose level is reached. The MTD and MAD of BI-1206 in combination with rituximab (at a fixed dose 375mg/m²) may be different to that of the single agent BI-1206 in Part A, Arm 1.

The RP2D from Part A, Arm 2 which will be used in Part B (Arm 2) of the clinical trial, will be determined by the Sponsor, Chief Investigator and Principal Investigators, following review of all relevant PK/PD and clinically relevant toxicity data for all patients entered onto the trial in Part A Arm 2, and the identified MTD or MAD. All significant toxicities and available data from the Part A Arm 1 and data from any other trials investigating BI-1206 will also be considered in the determination of the RP2D.

3.5 Patient evaluability

3.5.1 Response

All patients who meet the eligibility criteria, receive at least one administration of mAb (BI-1206 with/without rituximab) as part of this trial, have a baseline assessment of disease and at least one repeat disease assessment will be evaluable for response.

3.5.2 Safety

All patients receiving at least one administration of mAb (BI-1206 with/without rituximab) as part of this trial will be evaluable for safety.

3.5.3 Single Agent Dose escalation decisions (Part A, Arm 1)

Patients treated during the Part A, Arm 1 dose escalation phase of the trial who either receive four administrations of BI-1206 or experience a DLT will be evaluable for dose escalation and/or cohort expansion decisions in Part A, Arm 1.

Patients who receive less than 80% of their total planned induction doses (total across the four administrations) but complete the DLT period (Week 5) are not evaluable for dose escalation decisions (unless they have experienced a DLT).

Data from all patients who receive less than 4 doses of BI-1206 (single agent) and any available data from Part A, Arm 2 (if opened) will also be reviewed and taken into consideration at dose decision meetings. Data from any other trials investigating BI-1206 will also be considered in the dose escalation decisions.

For patients who do not receive the total full dose, please see [Section 6.2.5.6](#) for decision making on continuation of treatment. [Section 5.9.6](#) 'Dose delays/treatment discontinuation' also offers guidance for re-challenging patients post related AE observation.

